2. CGI-S
3. CHQ-PF28
4. PSI-4-SF
5. Caregiver-rated CGI-I
6. SNAP-IV Rating Scale

Safety and Tolerability Endpoints

1. Adverse events (AE)
2. Extrapyramidal symptoms (EPS) scales (Simpson-Angus Scale, Barnes Akathisia Scale, Abnormal Involuntary Movement Scale)
3. Clinical laboratory tests (Hematology, Chemistry and Urinalysis)
4. ECGs
5. Vital signs
6. Columbia Suicide Severity Rating Scale (C-SSRS)
7. Infrequent Behaviors Checklist

Sample size:

Based on results from the Phase 2 study, it is assumed that the average treatment difference between SPN-810 dose groups and placebo is 11.51 with a common standard deviation of 27.3. A sample size of 132 subjects per arm (264 subjects for 3 arms) will yield 90% power to detect a non-zero difference between the median of 18 mg or 36 mg dose group and the placebo using the Wilcoxon rank-sum test with a 2-sided significance level alpha=0.05.

It is assumed that approximately 20% of subjects will dropout before the completion of the study and hence, an adjusted total of 330 subjects will be randomized in a 1:1:1 ratio to obtain 264 subjects in the ITT population at the completion of the study.

The sample size was calculated using the nQuery Advisor Software, Version 7.

Analysis Populations:

Safety Population: will include all randomized subjects who received at least 1 dose of study drug.

Intent-to-Treat (ITT) Population: will include all subjects who received at least 1 dose of study drug and have a baseline and at least 1 valid post-randomization assessment of frequency of IA behaviors based on IA diary entry.

Per-Protocol (PP) Population: will include all of the subjects in the ITT population who completed the treatment period with 80% diary completion compliance and who did not have major protocol deviations.

PK population: will include all subjects in the safety population who had at least one PK sample drawn which had a quantifiable concentration for at least one analyte of interest.

Hypotheses:

Let μ_1 , μ_2 , and μ_3 represent the median percent change in the frequency of IA behaviors per 7 days in the Treatment period relative to the Baseline period in the ITT population for subjects treated with Placebo, 18 mg and 36 mg doses of SPN-810, respectively. The null (H_0) and the alternative (H_a) hypotheses are as in the following.

- $H_{01}: \mu_2 = \mu_1$, (there is no difference between the median of the 18 mg dose SPN-810 and the median of placebo) vs. $H_{a1}: \mu_2 \neq \mu_1$, (there is a difference between the median of the 18 mg dose SPN-810 and the median of placebo)
- $H_{02}: \mu_3 = \mu_1$, (there is no difference between the median of the 36 mg dose SPN-810 and the median of placebo) vs. $H_{a2}: \mu_3 \neq \mu_1$, (there is a difference between the median of the 36 mg dose SPN-810 and the median of placebo)

Handling Missing Data:

For the primary efficacy end point, the frequency of IA behaviors during the treatment period will be calculated over the number of days with non-missing IA diary data in the treatment period. No explicit imputation of missing data will be used, but this approach is implicitly equivalent to using the frequency of IA behaviors during the days with non-missing IA diary data to impute the frequency for days after study discontinuation and days with missing IA diary data.

Pharmacokinetic Methods:

Sampling:

5 blood samples divided between 2 visits.

Bioanalytical Analysis:

Pharmacokinetic Analysis:

Statistical Methods:

Summaries for continuous variables will include the sample size, mean, and standard deviation, median, minimum, and maximum. Summaries for discrete variables will include the tabulation of frequencies and percentages.

The primary efficacy analysis will be based on the ITT population. The primary efficacy endpoint is the percent change in the frequency (unweighted score) of IA behaviors per 7 days in the Treatment period relative to the Baseline period in the ITT population calculated over the number of days with non-missing IA diary data.

The primary efficacy analysis will be performed using the Wilcoxon rank-sum test to compare the medians of each of the two doses of SPN-810 (18 mg and 36 mg) with the median of the Placebo. The Hodges-Lehmann estimate and the associated 95% confidence interval (CI) will be calculated. The robustness of the primary analyses will be checked by performing two sensitivity analyses.

Each one of the six secondary endpoints will be analyzed using the analysis of covariance method based on the ITT population with missing data imputed using the Last Observation Carried Forward (LOCF) method. The model includes treatment and baseline as fixed independent covariates and change from baseline to final maintenance visit as a response variable. The least squares mean of each treatment group, the difference in the least squares mean (18mg dose minus placebo and 36 mg dose minus placebo), and the 2-sided 95% CI for the difference will be obtained.

Interim analysis:

A single interim analysis will be performed after approximately 50% of the randomized subjects complete the study. The main purpose of the interim analysis is to re-estimate the sample size.

Safety analysis:

Safety analyses will be based on the safety population. All AEs will be coded using the Medical Dictionary for Regulatory Activities (MedDRA) and will be summarized using discrete summaries at the subject and event level by system organ class and preferred term for each treatment group. Similarly, treatment-emergent AEs will be summarized by severity and relationship separately. Vital signs will be summarized using descriptive statistics by treatment groups. The summary includes sample size, mean, and standard deviation, median, minimum, and maximum. Continuous laboratory parameters will be summarized similarly. If applicable, categorical laboratory tests will be summarized using number and percent of subjects by treatment groups. Data on infrequent behaviors will be listed.

TABLE OF CONTENTS

TITLE PAGE	1
SUMMARY OF CHANGES.....	4
CLINICAL PROTOCOL SYNOPSIS	18
TABLE OF CONTENTS	24
LIST OF TABLES AND FIGURES	28
LIST OF ABBREVIATIONS	29
1 INTRODUCTION	31
1.1 Background	31
1.2 Sponsor's Phase 2a Study.....	32
1.3 Sponsor's Phase 2b Study.....	33
1.4 Impulsive Aggression Diary (IA Diary)	34
1.5 Study Rationale	34
2 STUDY OBJECTIVES	34
2.1 Primary Objective	34
2.2 Secondary Objectives.....	35
2.3 Tertiary Objective	35
3 INVESTIGATIONAL PLAN	35
3.1 Rationale for Study Design, Including Choice of Treatment Groups, Appropriateness of Measurements.....	35
3.2 Overall Study Design and Plan	36
3.2.1 Pre-Treatment Phase	36
3.2.1.1 Screening Period	36
3.2.1.2 Baseline Period.....	37
3.2.2 Treatment Phase.....	38
3.2.2.1 Randomization	38
3.2.2.2 Titration Period	38
3.2.2.3 Maintenance Period.....	38
3.2.3 Conversion/Taper Phase	38
3.2.4 End of Study / Early Termination	38

10.11 Child Health Questionnaire Parent Form 28-item (CHQ-PF28)	221

10.12 Parenting Stress Index-Short Form (PSI-4-SF)	225
--	-----

LIST OF TABLES AND FIGURES

Table 1: Schedule of Visits and Procedures	43
Table 2: Dosing Schedule (Total Daily Dose).....	50
Table 3: Clinical Laboratory Tests	60
Figure 1: Treatment Schedule (Conversion)	39
Figure 2: Treatment Schedule (Taper)	40

LIST OF ABBREVIATIONS

ADHD	Attention-Deficit Hyperactivity Disorder
AE	Adverse Event
AESI	Adverse Event of Special Interest
AIMS	Abnormal Involuntary Movement Scale
ASD	Autism Spectrum Disorder
BID	Twice a Day
CFR	Code of Federal Regulations
CGI-S	Clinical Global Impression – Severity of Illness
CGI-I	Clinical Global Impression – Global Improvement
CHQ-PF 28	Child Health Questionnaire Parent Form 28-item
CL/F	Apparent Clearance
CRA	Clinical Research Associate
CRO	Contract Research Organization
C-SSRS	Columbia Suicide Severity Rating Scale
eCRF	Electronic Case Report Form
EPS	Extrapyramidal Symptoms
FOCBP	Females of Childbearing Potential
IA	Impulsive Aggression
IAF	Informed Assent Form
ICF	Informed Consent Form
ICH	International Conference on Harmonization
IEC	Independent Ethics Committee
IRB	Institutional Review Board
ITT	Intent to Treat
KBIT-2	Kaufman Brief Intelligence Test, Second Edition
K-SADS-PL 2013	Schedule for Affective Disorders and Schizophrenia for School-aged Children – Present and Lifetime Versions 2013
LSM	Least-square Means
MAR	Missing at Random
MedDRA	Medical Dictionary for Regulatory Activities
MI	Multiple Imputation
MNAR	Missing Not at Random
ODD	Oppositional Defiant Disorder
PK	Pharmacokinetic(s)
PSI-4-SF	Parenting Stress Index – Short Form
QD	Once a Day
R-MOAS	Retrospective Modified Overt Aggression Scale
SAE	Serious Adverse Event

SAP	Statistical Analysis Plan
SM	Study Medication
SNAP-IV	Swanson, Nolan and Pelham Rating Scale - Revised
TDD	Total Daily Dose
ULN	Upper Limit of Normal
V/F	Apparent Volume of Distribution

1 INTRODUCTION

1.1 Background

Behavior with the immediate intent to cause harm – whether to self, others, objects, or property – constitutes aggression. Aggressive behavior becomes maladaptive when it persists, occurs outside an acceptable social context, and is of an intensity, frequency, severity and/or duration detrimental to the child's interests (Connor 2006; Jensen 2007). Maladaptive aggression is an expression of central nervous system dysfunction and may therefore be amenable to treatments targeting its neurobiologic substrate.

Aggression can be categorized into two broad subtypes based on the aggressor's motivation – 1) reactive or impulsive and 2) proactive or instrumental (Vitiello 1997). Impulsive aggression (IA) is angry, retaliatory aggression arising out of frustration, annoyance, or hostility to real or perceived provocations – stressors that youth of the same age typically experience with equanimity. IA is therefore an unplanned and immediate response reflecting out-of-control emotionality that satisfies immediate emotional pressures, albeit with negative consequences to the aggressor. In contrast, instrumental aggression is consciously planned, goal-oriented behavior with the specific intent of benefiting the aggressor (Jensen 2007).

IA is a common comorbidity in attention-deficit/hyperactivity disorder (ADHD) and is often refractory to primary ADHD therapy. In the Multimodal Treatment of Children with ADHD (MTA) study (MTA 1999), 54% of preadolescent study participants with ADHD Combined subtype displayed clinically significant aggression at baseline. Of these, 44% remained significantly symptomatic in terms of aggressive behavior after 14 months of optimal medication (stimulants) with/without behavioral therapy (Jensen, 2007).

IA amplifies the psychological, academic, emotional, and social problems associated with ADHD (Shelton, 1998), markedly increasing the risk of persistent behavioral problems, conduct disorder, encounters with the justice system, deficits in academic achievement, behavioral and disciplinary problems at school, and substance experimentation/abuse. Early-onset, pervasive and unremitting IA in the context of impulsive thoughts, emotional lability, and impulsive behavior is thought to represent a high-risk profile for progression from childhood ADHD to adult antisocial disorders (McKay, 2001). In the context of ADHD it represents a serious clinical and public health concern and warrants effective and timely intervention.

Since primary ADHD therapy has limited effect on IA, a stepped-care approach has been recommended, with aggression-targeted therapy such as an antipsychotic added to ADHD therapy to manage residual aggressive behaviors (Scotto- Rosato 2012). Risperidone and other “atypical” antipsychotics have historically been at the forefront of treatment recommendations regarding combination therapy for managing comorbid aggression in children with ADHD (Pappadopoulos et al. 2003; Pliszka et al. 2006; Pliszka et al. 2007). However, only two double-blind randomized placebo-controlled trials of risperidone as adjunctive therapy in children with ADHD and aggression refractory to stimulants have been published – 1) a pilot study in 25 children that was likely underpowered and did not detect a significant treatment effect (Armenteros 2007; Aman 2014) and 2) the recently completed TOSCA (Treatment of

Severe Childhood Aggression) study (Farmer et al. 2011; Aman 2014; Gadow 2014). The effect size for risperidone's effect on IA was small (0.29), even though the dosage could be adjusted to optimal effect. The TOSCA study provides initial empirical evidence supporting a stepped-care approach in which ADHD children with severe aggression are initially treated with primary ADHD therapy followed by adjunctive antipsychotic therapy targeted to IA. However, the long-term effects of risperidone and similar antipsychotics in terms of metabolic derangements predictive of diabetes and cardiovascular disease, have become cause for considerable concern, especially in the face of very limited evidence of efficacy as aggression-targeted therapy in ADHD. The TOSCA study confirmed that stimulant co-therapy does not attenuate the adverse effects of risperidone or similar agents on body composition, metabolic parameters, prolactin, or sedation (Calarge 2009; Penzner 2009).

Molindone hydrochloride (molindone) is a medium potency antipsychotic, and is currently under development by the Sponsor as an extended-release formulation (SPN-810), for its potential utility in treating IA in children with ADHD.

In an open-label study, molindone improved aggressive behavior in children (N=6, 6-11 years of age) with undersocialized conduct disorder, aggressive type (Greenhill 1981). The optimum dose was 0.5 mg/kg/day. Molindone was also shown to be effective in treating aggressive behavior in a double-blind, 8-week, inpatient study of 31 children, ages 6 to 11, with undersocialized conduct disorder, aggressive type (Greenhill 1985).

Prior to its withdrawal from the US market for commercial reasons, Immediate-Release Molindone (Moban®) was approved for the treatment of schizophrenia in adults and adolescents. Its use was also evaluated in a pediatric population with early-onset schizophrenia and schizoaffective disorder when it was selected as the first-generation antipsychotic on the basis of its more favorable safety profile for comparison with second-generation agents (risperidone, olanzapine) in an NIH-sponsored study (TEOSS, Treatment of Early-Onset Schizophrenia Spectrum Disorders Study) (McClellan 2007). At an average dose of 60 mg/day (range, 10-140 mg/day), molindone was shown to be safe and well-tolerated (Sikich 2008). Molindone (10-140 mg/day) was not associated with significant increases in weight/BMI (in contrast to olanzapine). Molindone was also not associated with more dystonic or parkinsonian symptoms when given with benztrapine, although akathisia was reported by more molindone-treated subjects. Results of randomized controlled trials such as TEOSS stimulated interest in the potential usefulness of molindone as a weight- and metabolically-neutral D2-receptor antagonist in children with ADHD and comorbid IA.

1.2 Sponsor's Phase 2a Study

Study 810P201, was a proof-of-concept, multicenter, open-label, parallel-group, randomized, dose-ranging, safety, and tolerability study of molindone administered as experimental Molindone Immediate Release (IR) capsules in children with ADHD and persistent serious conduct problems (Stocks 2012).

Target subjects were healthy male or female children aged 6 to 12 years, inclusive, with a diagnosis of ADHD accompanied by persistent serious conduct problems. A total of 78 subjects (19-20 per treatment group) in ten U.S sites were randomized. The primary objective was to evaluate the safety and tolerability of four weight-based dosages of Molindone IR dosed three times daily in children with ADHD.

This document is confidential. It contains proprietary information of Supernus® Pharmaceuticals, Inc. Any viewing or disclosure of such information that is not authorized in writing by the Sponsor is strictly prohibited. Such information may be used solely for the purpose of reviewing or performing this study.

and persistent serious conduct problems (<30 kg: [REDACTED]/day; ≥30 kg: [REDACTED] mg/day). The secondary objectives were to 1) explore the relationship between molindone plasma concentration exposure and safety/tolerability endpoints and 2) assess the effect of Molindone IR after 6 weeks of maintenance treatment in reducing persistent serious conduct problems as measured by the Conduct Problem Subscale of the Nisonger Child Behavior Rating Form-Typical Intelligence Quotient (NCBRF-TIQ).

[REDACTED]
[REDACTED]
[REDACTED]

1.3 Sponsor's Phase 2b Study

Sponsor completed a Phase 2b multicenter, randomized, double-blind, placebo-controlled trial in the United States in pediatric subjects 6 to 12 years of age diagnosed with ADHD and IA that was not controlled by optimal stimulant and behavioral therapy (Sponsor Study 810P202). The primary objective of the study was to assess the effect of an extended-release tablet formulation of molindone hydrochloride (SPN-810) (12 to 54 mg/day) in reducing IA as measured by the Retrospective-Modified Overt Aggression Scale (R-MOAS) after at least three weeks of assigned treatment. Secondary endpoints included the rate of remission of IA and measurement of the effectiveness of SPN-810 on Clinical Global Impression (CGI) and ADHD scales as well as evaluation of the safety and tolerability of the drug. Patients who completed the study were offered the opportunity to continue into an open-label phase of six months duration.

SPN-810 dose within treatment groups was stratified by weight (below/above 20 kg). Both the medium (24/36 mg) and low (12/18 mg) dose groups showed statistically significant difference from the placebo group in the change from baseline to Visit 10 in R-MOAS but the high (36/54 mg) dose group was not significantly different from the placebo group. Furthermore, both the low dose and medium dose groups were significantly different from the high dose based on pair-wise comparison among the dose groups.

[REDACTED]
[REDACTED]
[REDACTED]
[REDACTED]
[REDACTED]

[REDACTED]
[REDACTED]
[REDACTED]
[REDACTED]
[REDACTED]

1.4 Impulsive Aggression Diary (IA Diary)

Sponsor has developed and validated a new measurement tool to assess behaviors associated with IA. The impulsive aggression diary (IA diary) is an electronic observer-reported outcome (eObsRO) instrument that comprises an episodic diary (to be reported as soon as possible after the parent or other guardian or observer witnesses the child's IA behavior) and an evening diary (to enable at a minimum, completion of the diary once each day). The IA diary monitors the frequency of occurrence of 15 IA behaviors: Yelling, Screaming, Threatening, Scratching, Throwing, Slamming, Hitting Self, Arguing, Cursing, Name Calling, Shoving, Hair Pulling, Fighting, Hitting Others, Kicking Others. The development process followed FDA's "Guidance for Industry Patient-Reported Outcome Measures: Use in Medical Product Development to Support Labeling Claims." Through this process, the IA diary was demonstrated to be a psychometrically valid and reliable tool to assess IA in children (Sponsor Study 810P501).

1.5 Study Rationale

The results of the Phase 2b study indicated that doses ranging from [REDACTED]/day were safe, effective and well tolerated. This Phase 3 study seeks to demonstrate the efficacy, safety, and tolerability of SPN-810 in the treatment of IA in patients with ADHD in conjunction with standard ADHD treatment. Study medication (SM) will be given as a divided dose twice daily (BID) with or without food. A randomized, placebo-controlled, double blind, multicenter, parallel group, fixed dose study design will be used. Frequency of IA behaviors will serve as a proxy for IA severity. The IA diary will be used to assess the frequency of IA behaviors. The IA diary was developed and validated for use as a contemporaneous, event-driven, observer-reported outcome measure. It monitors behaviors that have been specifically linked to IA. It does not rely on long periods of recall or subjective weighting of behaviors. For these reasons, the IA diary is uniquely suited to detect changes in the frequency IA behaviors, which in turn is indicative of the severity of IA.

Additionally, IA severity and improvement will be assessed using Clinical Global Impression (CGI) scales completed by both investigator and caregiver. Subject and caregiver quality of life will also be evaluated.

The effect of molindone on body composition, metabolic parameters, and prolactin will be evaluated. Emergence of extrapyramidal symptoms will be monitored.

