5.4.4 Laboratory Measurements

With the exception of urine pregnancy test, clinical laboratory tests will be performed by a central laboratory as specified in the reference binder.

Details for collecting, handling, and shipping samples (including shipment addresses) will be detailed in a separate laboratory manual. The Schedule of Visits and Procedures ([Table 1](#)) shows the time points at which urine samples will be collected for urinalysis and blood samples will be collected for clinical laboratory tests and plasma concentration levels.

[Table 3](#) presents the clinical laboratory tests to be performed. Metabolic parameters (including insulin, glucose, triglycerides, and cholesterol) and prolactin will be measured. A subject will be excluded if the Screening blood test results indicates > 2 times the upper limit of normal (ULN) of alanine

aminotransferase (ALT), aspartate aminotransferase (AST), gamma glutamyl transpeptidase (GGT), and/or serum creatinine. Laboratory tests will not be repeated for these subjects.

All laboratory tests will be reviewed in a timely manner by qualified site personnel to ensure safety. Abnormal lab findings may be confirmed if necessary by one repeated testing at the discretion of the Investigator. Any repeat laboratory testing will be conducted under **fasting condition**. Any laboratory abnormality may qualify as an AE in the Investigator's judgment.

A total of approximately 42 mL of blood per subject will be drawn during the study: 22 mL is for clinical laboratory tests and 20 mL is for PK sampling.

Table 3: Clinical Laboratory Tests

Category	Parameters
Hematology	RBC, WBC, Hgb, HCT, MCH, MCHC, MCV, platelet count, and WBC with differential (neutrophils, lymphocytes, monocytes, eosinophils, basophils, large unstained cells)
Chemistry	Electrolytes: Na ⁺ , K ⁺ , chloride, bicarbonate
	Liver function tests: alkaline phosphatase, AST, ALT, total bilirubin, direct bilirubin, indirect bilirubin
	Renal function parameters: BUN, creatinine
	Other: glucose, Ca ⁺² , albumin, phosphorus, lactate dehydrogenase, total protein, CK/CPK, globulin, uric acid, triglycerides, insulin, prolactin, cholesterol – total, HDL and LDL Amylase, gammaGT (GGT), Iron, Lipase, Magnesium
Urine	Urinalysis Urine Drug Screen Urine pregnancy test (FOCBP only)

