6.14.3 Vital Signs, Height and Weight

Vital signs will be summarized by visit by treatment group using descriptive statistics. Both actual values changes from baseline to visit will be summarized. Descriptive summary statistics (mean, SD, median, and range) for vital sign data, height, weight and BMI will be evaluated by treatment group.

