6 STATISTICAL METHODS

6.1 *General Methodology*

All statistical analyses will be conducted using SAS Version 9.4 or later on the Microsoft® Windows Operating System.

All tabulations of analysis results will include summaries for the three treatment groups: SPN810 █ mg, SPN810 █ mg and placebo.

Continuous data will be summarized using n (number of subjects with non-missing observations), mean, median, standard deviation (SD), minimum value, and maximum value. Categorical data will be summarized using the frequency count and percentage (n, %) of subjects in each category. Number of subjects with non-missing values or number of subjects with missing values (e.g., Not Done) will be presented, where appropriate. Subjects with missing values will not contribute to the denominator of percentage calculations. Counts of zero in any category will be presented without percentage.

Treatment differences will be evaluated as SPN-810 dose minus placebo. Unless otherwise specified, all statistical hypothesis tests will be 2-sided with a significance level of $\alpha=0.05$. All confidence interval will be calculated 2-sided from the unadjusted 5% significance level. P-values will be reported to 4 decimal places. P-values <0.0001 will be presented as " <0.0001 ". Similarly, p-values >0.9999 will be presented as " >0.9999 ".

The precision rules for the presentation of summary statistics will be:

- Sample size (n, N) and number of missing responses (if displayed) – Integer
- Mean, median, percentiles, and confidence interval – One additional decimal place than reported/collected
- Standard deviation – Two additional decimal places than reported/collected
- Minimum, maximum – Same number of decimal places as reported/collected
- Ratios – two decimal places
- Percentages – one decimal place generally, or two decimal places for $<0.1\%$

The data summaries will be accompanied by individual subject data listings. All data available from diary, eCRF, and external transfer (labs) will be listed and will include relevant and pertinent subject information, e.g., treatment, center, age/gender/race, and study day. The listings will be

sorted in the order of treatment group, unique subject ID, and assessment date/time and assessment name. The unique subject ID consists of 3-digit study number followed by []-digit site number and []-digit subject number separated by hyphen (e.g., []).

For each summary table, a supporting listing will be identified in the footnote.

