7.8.2 *Laboratory Test*

Clinical laboratory values will be summarized by treatment group and visit using descriptive statistics for hematology, biochemistry, and urinalysis. For quantitative laboratory parameters, both actual values and change from baseline values will be summarized (Table 14.3.2.1, Table 14.3.3.1, and Table 14.3.4.1).

Laboratory test result will be assigned a low, normal, high (LNH) classification according to whether the value is below (L), within (N), or above (H) the reference range provided by the laboratory. Within-treatment comparisons will be based on three by three tables (shift tables), that, for a particular laboratory test, compare the LNH classification at baseline to the LNH classification at visit. By subject-listings of all laboratory values will be provided for subjects who have L or H classification in any of their laboratory tests (Table 14.3.2.2, Table 14.3.3.2, and Table 14.3.4.2).

Note the summary and shift tables will only use the planned/scheduled tests. However, both scheduled and repeat tests will be in the data listing.

A complete lab data listing, including hematology, biochemistry, and urinalysis will be provided for all subjects. Investigator assessment of clinical significance is based on the local laboratory reference ranges (Listing 16.2.3.2.1 – Listing 16.2.3.2.3).

7.8.3 *Vital Signs, Height, Weight, and BMI*

Vital signs (body temperature, heart rate, respiration rate, systolic blood pressure, and diastolic blood pressure), and their changes from baseline will be summarized by treatment group and

visit (Table 14.3.5, Listing 16.2.3.3). Subject body size (weight, height, and BMI) will be summarized similarly (Table 14.3.6, Listing 16.2.3.4).

7.8.4 12-Lead ECG

By-visit tabular summaries of the quantitative ECG parameters and the overall ECG findings (normal, abnormal not clinically significant, or abnormal clinically significant) will be presented. The QT interval will be corrected using Fridericia's method.

ECG results will be summarized by visit by treatment group using descriptive statistics (for quantitative ECG parameters) and frequency tables (for qualitative ECG parameters, including the overall ECG finding). For quantitative ECG parameters, both actual values and change from screening values will be summarized (Table 14.3.7.1 and Table 14.3.7.2).

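### The protocol says the drug's effect on body composition, metabolic parameters and prolactin will be evaluated, but no dose-minus-placebo estimate or confidence interval is specified for these variables

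*Protocol*

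**What the plan says.** **Intent.** Protocol 1.5 (Study Rationale): "The effect of molindone on body composition, metabolic parameters, and prolactin will be evaluated". Protocol 1.1 gives the background: earlier trials raised interest in molindone as a "weight- and metabolically-neutral D2-receptor antagonist in children with ADHD and comorbid IA".

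**Measurement.** Protocol 5.4.4: "Metabolic parameters (including insulin, glucose, triglycerides, and cholesterol) and prolactin will be measured". Chemistry is taken at Visits 1, 3, 6 and 7. Weight, height and BMI are recorded at Visit 1 and at Visits 3 to 7. Protocol 4.2.7 applies the Visit 7 procedures, which include both, to children who discontinue early.

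**Laboratory analysis.** SAP 7.8.2 summarizes values by arm and visit: "For quantitative laboratory parameters, both actual values and change from baseline values will be summarized". The only comparison it names is this: "Within-treatment comparisons will be based on three by three tables (shift tables". Protocol 6.14.2 says the same.

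**Body size analysis.** SAP 7.8.3, after describing vital signs and their changes from baseline by arm and visit: "Subject body size (weight, height, and BMI) will be summarized similarly". Protocol 6.14.3: "Descriptive summary statistics (mean, SD, median, and range) for vital sign data, height, weight and BMI will be evaluated by treatment group".

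**General rules.** SAP 6.1 puts all three arms in every tabulation and gives n, mean, median, SD, minimum and maximum for continuous data. It adds: "Treatment differences will be evaluated as SPN-810 dose minus placebo".

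**The concern.** In a randomized trial, the effect of a drug is a contrast with placebo. The children are 6 to 12 years old, so growth can raise weight in every arm. Fasting is stated only for repeat laboratory tests (Protocol 5.4.4), so sampling conditions at scheduled visits may add noise to glucose, insulin and triglycerides. The placebo arm is there to absorb both influences, and the contrast with it is what measures the drug.

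The plan collects what that contrast needs and tabulates the ingredients, but it stops before the estimate. The study report would then give mean changes in three columns, with no prespecified statement of how large a weight, metabolic or prolactin effect the data are compatible with. Any such statement would have to be put together after unblinding, with the choices of adjustment, scale and handling of early discontinuers still open.

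**Working it through.** **Step 1: look for a between-arm estimate.**

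| Place | What is specified for these variables | Dose-minus-placebo estimate? |
|---|---|---|
| Protocol 6.14.2 | Descriptive summaries by visit and arm; within-arm shift tables | No |
| Protocol 6.14.3 | Descriptive summaries by arm | No |
| SAP 7.8.2 | Actual values and change by arm and visit; within-arm shift tables | No |
| SAP 7.8.3 | Actual values and change by arm and visit | No |
| SAP Appendix 2, Tables 14.3.3.1, 14.3.3.2, 14.3.6 | Titles name change from baseline, or shift from baseline classification | No |
| SAP 6.1 | Sign of treatment differences; two-sided unadjusted intervals | General rule; names no safety variable |
| SAP 7.8.5 (C-SSRS) | Each dose against placebo by Fisher's exact test | Test only, and for suicidality |

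The last row matters. Where the SAP plans a safety comparison with placebo, it says so in the section concerned. Sections 7.8.2 and 7.8.3 contain no such sentence.

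**Step 2: precision of the missing estimate.** The documents state no precision, power, margin or SD for these variables, so there is no figure of theirs to reproduce. With a common SD of the change and n per arm:

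- SE of the difference = SD × √(2/n)
- 95% half-width = 1.96 × SE

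| n per arm | Source | √(2/n) | Half-width, in SD of change |
|---|---|---|---|
| 88 | Protocol 6.10: 264 in total ÷ 3 | 0.151 | 0.295 |
| 122 | SAP 3.5, before the dropout allowance | 0.128 | 0.251 |
| 153 | SAP 3.5, randomized | 0.114 | 0.224 |

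Protocol 6.10 also states 132 per arm, which does not agree with its total of 264 for three arms (132 × 3 = 396). At 132 the half-width would be 0.241 SD, inside the range above.

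These figures are for an unadjusted difference in mean change. Adjusting for baseline should narrow them, by an amount that depends on a correlation the documents do not give. For variables analysed on the log scale, the SD is that of the log change and the result reads as a ratio.

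**Step 3: scale, as an illustration only.** If the SD of weight change over the treatment phase were 0.8 to 1.5 kg (an assumption), the half-width would run from 0.224 × 0.8 = 0.18 kg to 0.295 × 1.5 = 0.44 kg.

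**The case against.** The strongest reply is that descriptive safety reporting is normal and that little is lost here. Mean changes are tabulated by arm beside placebo, so a rise in prolactin or lipids that stays inside the reference range would be visible. A crude difference and interval can be computed from the tabulated n, mean and SD. This stands, and it limits the point. A reader might infer from the shift-table sentence that laboratory values are examined only inside each arm and that smaller rises disappear. The documents do not support that: the shift tables supplement the continuous summaries, and no within-arm comparison is named for body size at all. Nor would it help to set the power of comparing out-of-range proportions against that of comparing means, since the SAP plans neither test and already tabulates the means.

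A second reply is that neutrality is not an objective, hypothesis or listed safety endpoint. This is also right: it appears only as background in Protocol 1.1.

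A third reply is that SAP 6.1 already covers treatment differences. This is weaker. The sentence fixes a direction, and neither 7.8.2 nor 7.8.3 applies it.

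Finally, SAP Appendix 3 (table shells) is only a heading in the text available, so a difference column there cannot be ruled out. The SAP body and the table titles give no sign of one.

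What a reader cannot recover from side-by-side columns is a baseline-adjusted estimate, a log-scale analysis of variables likely to be skewed, or the standing of a prespecified result.

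**Conclusion.** The gap is real but modest. Protocol 1.5 undertakes to evaluate the drug's effect on these variables, and the specified analysis describes the arms without estimating that effect. The shortfall is in the planned analysis and not in the data, which could bound each effect to within about 0.22 to 0.30 SD of the change before adjustment. That range assumes 88 to 153 children per arm with usable values and a common SD.

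A reader might go further and conclude that the trial sets out to show metabolic neutrality and will fail to do so. The documents do not support this, because no neutrality claim is planned. The added intervals would not supply one either: they would say how large an effect is compatible with the data, while a finding of neutrality would also need a margin, and none is set. The point is a cheap improvement to the reporting of something the protocol singles out. It does not touch the efficacy conclusions.

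**What to change.** Add one table, specified in SAP 7.8.2 and 7.8.3 before unblinding.

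- **Variables:** weight; BMI, also as an age- and sex-standardised score; prolactin; glucose; insulin; triglycerides; total, HDL and LDL cholesterol.
- **Model:** ANCOVA of the on-treatment value on arm and the baseline value, with prolactin, insulin and triglycerides on the log scale.
- **Value used:** Visit 6 or, for early discontinuers, the last post-baseline value. For the laboratory variables this will usually be the sample from the end-of-study visit. It may follow the last full dose, so report how many values per arm come from this source.
- **Output:** each dose minus placebo with a 95% interval, labelled as estimation without multiplicity adjustment.
- **Note to the table:** the intervals bound the effect and do not by themselves establish neutrality, since no margin is set.

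Protocol 1.5 speaks of body composition, but only weight, height and BMI are collected, so the table should use the SAP's term, body size.

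**Cost:** a paragraph of SAP text and one table, with no new data, visits or alpha. The downside is ten unadjusted intervals per dose (weight, two for BMI, prolactin, glucose, insulin, triglycerides and three for cholesterol), or twenty in all. Some may exclude no difference by chance, so the descriptive label matters.
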